## Pain Score Assessment

 Subjects will rate their pain using the Wong-baker FACES scale (Garra 2010) and a numerical rating scale (NRS) before and after the procedure. The NRS score ranges from 0-10 where 0 is no pain and 10 is the worst pain imaginable (Williamson 2005).

## • Quality of Life Assessment

 Subjects 6-11 years of age will use the Children's Dermatology Quality of Life Index (cCDLQI) at each visit (Lewis-Jones 1995). Subjects 12-17 years of age will use the Teenager's Quality of Life Index (T-QoL) at each visit (Basra 2018). Assessments should be performed prior to ILTA administration when applicable.

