## Objectives

- Primary Objectives
  - Validate patient tolerability of needle-free delivery of intralesional triamcinolone using patient-reported outcome measures.
- Secondary Objectives
  - Validate efficacy of needle-free delivery of intralesional triamcinolone for pediatric alopecia areata.
  - Assess the impact of needle-free delivery of intralesional triamcinolone on quality of life for pediatric alopecia areata.

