## **Inclusion and Exclusion Criteria**

	Inclusion Criteria					
	Subjects must meet all of the following criteria to be eligible for this study:	Yes	No			
1	6-17 years of age.					
2	Diagnosed with alopecia areata by either: • A board-certified dermatologist, OR • Dermatology Nurse Practitioner, OR • Skin punch biopsy					
3	
 
Patient has at least 2 alopecic patches each measuring at least 2 cm^2 and are
 
Located on contralateral body sites OR
 
Within the same body site but separated by ≥ 1 cm
 
					
4	Patient is a candidate for intralesional triamcinolone.					
4	Patient able to give informed assent under IRB approval procedures when appropriate.					
5	At least one parent or guardian is able to provide informed consent.					

	Exclusion Criteria				
	A patient who meets any of the following criteria will be excluded from the study.	Yes	No		
1	Patient has alopecia totalis, alopecia universalis, or alopecia areata with ophiasis pattern.				
2	Known allergy or hypersensitivity to triamcinolone acetonide				
3	Pregnant, breastfeeding, or planning to get pregnant 4 weeks before, during, and 4 weeks after the study.				
4	Patient is unable/unwilling to provide informed assent when applicable.				
5	Known medical diagnosis or use of a medication that alters pain response at time of injection.				
6	Active infection at site designated for injection.				
7	If currently being treated for alopecia areata, the current treatment regimen has been started within less than 4 weeks of screening.				

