## **Number of Research Participants**

This is a proof-of-concept pilot study. Collins et al. stated that the boundary between mild and moderate pain is a numerical rating scale (NRS) score of 3 (Collins 1997). Previous use of needle-free delivery methods have demonstrated an NRS < 3 (Nantel-Batista 2017, Vadeboncoeur 2017). Based on previous studies and the pilot nature of this study, 15 subjects will be enrolled to determine whether mild or moderate pain would be anticipated in future large scale assessments.

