## Data Analysis Plan

Statistical analyses will be completed under the supervision of a statistician. Statistical analysis will be done by statistical software (e.g. SPSS, SAS, R, Excel; etc.) AUROC will be calculated in order to assess for accuracy. The  $\chi^2$  test may be used for comparison of dichotomous variables, and the Mann-Whitney test may be used for non-normally distributed continuous variables. The cutoff value for significance was set at p = 0.05.

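### The age that decides the quality-of-life form is not fixed at baseline, and the only test named for such scores ignores each child's own baseline

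*Combined protocol and SAP*

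**What the plan says.** The Objectives section sets one secondary QoL objective for the whole sample: "Assess the impact of needle-free delivery of intralesional triamcinolone on quality of life for pediatric alopecia areata".

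The Quality of Life Assessment section serves it with two instruments. "Subjects 6-11 years of age will use the Children's Dermatology Quality of Life Index (cCDLQI) at each visit", and those aged 12-17 the Teenager's "Quality of Life Index (T-QoL) at each visit". It adds that the forms should be completed before the injection where one is given. It says nothing on which date fixes a child's age group.

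The Data Analysis Plan names no QoL endpoint, time point or summary, and no rule for two instruments. For continuous scores it offers one test: "the Mann-Whitney test may be used for non-normally distributed continuous variables". The other test named, chi-square, is for dichotomous variables. A general cutoff of p = 0.05 is given.

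The Data to be Collected list describes the QoL data as DLQI plus the patient survey. DLQI is neither of the two instruments above.

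**The concern.** Two things look unsettled.

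**Which age counts.** A coordinator holding the age rule at Week 8 or Week 12, with a child who has just turned 12, can reasonably hand over either form. If the form changes, that child has a baseline on one scale and an endpoint on another. The difference means nothing, and the lost score cannot be recovered after the visit.

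**How the scores are compared.** The study has one group of children, each measured at baseline and at Weeks 4, 8 and 12. The natural QoL question is how each child changes. Mann-Whitney treats the two sets of scores as coming from different children, so it discards the pairing. QoL has no second independent group to compare either: the treated and untreated patches belong to the same child, and the two age groups are on different scales.

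**Working it through.** **Inputs from the protocol**
- Sample size: "15 subjects will be enrolled to determine whether mild or moderate pain would be anticipated in future large scale assessments". This rests on pain; no QoL sample size, SD or target change is given, so there is no QoL figure to reproduce.
- Age range: "6-17 years of age", i.e. 12 one-year bands, six for each form. No age quota is given.
- Follow-up: 12 weeks from baseline, with a visit window printed as + 7 days, so up to 13 weeks.

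**Assumptions (not in the documents)**
- Ages are spread evenly over the 12 bands.
- Current age governs the choice of form.

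**1. How often would a child change form?**

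The chance that one child's 12th birthday falls within *w* weeks of baseline is *w* / (52.18 × 12).
- 12 weeks: 12 / 626.2 = 0.0192 per child. Expected number: 15 × 0.0192 = 0.29. Chance of at least one: 1 − (1 − 0.0192)^15 = 0.25.
- 13 weeks: 13 / 626.2 = 0.0208 per child. Expected number: 0.31. Chance of at least one: 0.27.

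Without the even-age assumption, the result depends on how many 11-year-olds enrol. Each has a 12 / 52.18 = 23% chance of turning 12 within 12 weeks. With no 11-year-olds the problem does not arise. Even ages give 15 / 12 = 1.25 of them, and 1.25 × 0.23 = 0.29, as above.

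**2. How many children inform each form?**

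Treat the number on one form as Binomial(15, *p*).
- *p* = 0.5: mean 7.5, central 95% range 4 to 11. A 7/8 split has only a 39% chance.
- *p* = 0.4 or 0.6: expected split 6/9.
- *p* = 0.3 or 0.7: expected split 4.5/10.5.

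**3. How precise is a paired estimate on one form?**

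The 95% CI half-width, in SDs of the within-child change, is t(0.975, n − 1) / √n.

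| Children on the form | Half-width (SD of change) |
|---|---|
| 4 | 1.59 |
| 7 | 0.92 |
| 8 | 0.84 |
| 11 | 0.67 |
| 15 (if all shared one scale) | 0.55 |

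**4. What does ignoring the pairing do?**

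Take the same variance σ² at both visits and correlation ρ between a child's two scores. The variance of the mean change is 2σ²(1 − ρ)/n. An independent-groups comparison behaves as if it were 2σ²/n. Whenever ρ is positive, as is usual for repeated scores on one child, the unpaired analysis overstates the uncertainty by the factor 1 / (1 − ρ) in variance. The documents give no ρ, so no figure is attached.

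**The case against.** The phrase about each visit most naturally gives the frequency of administration. Read that way, a child in the 6-11 group simply completes the same form every time, and no switch is planned. This stands: a reader might infer that the protocol makes children change form at 12, but it does not say so. What is missing is the reference age. Even under the less favourable reading, the chance that no child is affected is about 75%.

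The Mann-Whitney test is only one that may be used, and the complaint applies to the whole analysis section. That is fair. Still, nothing else is offered for these scores, and a reader following the plan would have no paired method.

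A reader might also infer that the QoL objective is tested at p = 0.05 and is underpowered. For an assumed change of 0.8 SD, a paired t-test has power 43% with 7 children, 50% with 8 and 82% with 15. The arithmetic is right, but the documents do not support the charge. The cutoff is generic, no QoL test or power is stated, the 0.8 SD has no source in the protocol, and 15 was chosen for pain in a proof-of-concept pilot.

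Nor does the plan make significance unreachable. The smallest two-sided p of 2 × 0.5^5 = 0.0625 with 5 children belongs to the signed-rank test, which the plan does not name.

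Finally, the protocol neither pools the two forms nor says they will be analysed apart, and 7-8 children on each is only the average under an even age mix.

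**Conclusion.** The point holds in a limited form. The reference age for choosing the form is undefined, and the one test named for such scores does not fit a single group measured repeatedly.

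The first gap puts few children at risk: about 0.3 expected and roughly a one-in-four chance of any, if ages are even and sites go by current age. Any loss would be irreversible and would fall on a form with few children. The second gap affects every child's QoL result if Mann-Whitney is used. Its size depends on a correlation that the documents do not give.

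QoL is a secondary objective of a pilot, so this is a worthwhile clarification rather than a threat to the study. It should be settled before the first child reaches a follow-up visit.

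**What to change.** 1. In Quality of Life Assessment, state that the form is chosen by the child's age on the day of the baseline visit and kept for all later visits.
2. In the Data Analysis Plan, replace Mann-Whitney for QoL with within-child change from baseline to Week 12: a paired estimate with its 95% CI, and a signed-rank test only if a test is wanted. Report each form separately, because raw scores on different scales cannot be combined. Call the results exploratory, given the small and unpredictable number on each form. The estimate and interval should lead, since the signed-rank floor of 0.0625 would apply to any form with 5 children.
3. Optionally, add one supportive analysis of all children: changes standardised within form, scoring direction aligned, in a signed-rank test stratified by form. It assumes that the two scales respond alike and relies on SDs from perhaps 7 children, so it should not replace item 2.
4. Reconcile the DLQI entry under Data to be Collected with the two named instruments. At the same time, reconcile QoL at screening, which Study Visits lists and the Study Timeline chart does not mark.

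The cost is a few sentences, with no added visits, children or forms. The small downside is that a child just past 12 finishes on the younger form.

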## • Patient Survey

 Participants will be given a survey at each visit. This will assess perceived tolerability, comfortability, associated fear, and assess experience and preference over conventional needle and syringe.

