## **Study Design**

This is an interventional pilot study assessing the tolerability of needle-free delivery administration of ILTA with the Med-Jet as an alternative to conventional syringe and needle in patients with patchy pediatric alopecia areata. There will be a total of four (4) or five (5) visits necessary for study participation. We hypothesize that the Med-Jet will have acceptable pain tolerability, efficacy, safety, and a positive impact on patient quality of life.

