## • Study Visits

There will be four (4) or five (5) visits necessary for study participation:

- If all inclusion criteria are met and no exclusion criteria are met on the same day and the patient and their guardian wish to start the study, the baseline visit and screening visit can be completed on the same day. This will decrease the number of visits from 5 to 4. o
- If the patient has complete hair growth prior to the end of the study, they will complete all remaining visits, but they will not receive injections.
- Visit 1 Screening (within 5 weeks prior to baseline visit or same day, estimated time 1 hour if baseline activities are not performed):
  - We will obtain informed consent, review inclusion/exclusion criteria, obtain medical history (medical conditions, surgeries, alopecia areata history, medications, allergies, social history, and relevant family history), obtain vitals, perform a complete skin exam, efficacy assessments, patientreported pain assessments, and quality of life assessments. A urine pregnancy test will be performed for persons of childbearing potential.
- Visit 2 Baseline (Week 0, estimated time 1.5 hours if not performed the same day as screening):
  - This will be the in-office intervention visit to be scheduled within 4-6 weeks of screening visit. We will review inclusion/exclusion criteria, obtain concomitant medications, adverse events (AE), obtain vitals, perform limited skin examination with efficacy assessment, photograph of target lesions, perform intervention injections per protocol, collect patientreported pain assessments and quality of life assessments. A urine pregnancy test will be performed for persons of childbearing potential.
- Visits 3-5 Follow up study period (Week 4, 8, and 12, estimated time 30 minutes each):
  - A limited skin exam, photographs, review of AEs and concomitant medications, efficacy assessments, QoL assessments and pain assessments will be performed. ILTA will be administered at each visit unless complete regrowth has occurred. A urine pregnancy test will be performed for persons of childbearing potential.

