## **Prior and Concomitant Medications and Therapies**

All medications and therapies being taken/used by the subject at the time of consent or at any time during the study will be recorded. All medications and therapies for alopecia areata, will be recorded. The stop dates and reason for stopping all medications and therapies prohibited in the study will be recorded.

- Intervention
  - At least two patches; each measuring 2 cm2 and at least 1 cm from one another will be identified, mapped out, and photographed.
  - Only one of the alopecic patches will be treated.
  - The concentration of ILTA will be controlled at up to 1 mg per cubic centimeter (0.1 ml
     @ a maximum concentration of 10mg/ml) injected every 1 cm until patch has been fully treated. The researcher providing treatment will be properly trained to deliver intradermal injections using the syringe and needle-free system.
  - Med-Jet with Triamcinolone (TAC) Procedure ILTA will be administered into the patches. The PI and co-investigators will be performing interventions and follow proper training by the manufacturer on operation and handling of the device. Training will consist of a live course with a designated manufacturer technician supplemented with training videos. A standard sterile disposable 5 ml syringe will be used to draw TAC using standard sterile protocol. This syringe will be attached to the Med-Jet along with a sterile barrel and disposable sterile tip. The target lesion will be wiped with alcohol and injected with up to 10mg/ml of TAC directed towards the dermis to create a blanching wheal that is 1 cubic centimeter (total of 0.1 ml of injected fluid). The optimal injection pressure used on the subject will start at 130 pounds per square inch (psi) and increased by 5 psi until a blanching wheal is observed. The optimal pressure until the targeted patch is completely treated.
  - Patients will be treated at each visit unless complete regrowth has occurred.
     Photographs will be taken at each visit and activities will be completed as above.

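### Preference over needle and syringe is asked of every child, but no needle injection is given, prior needle ILTA is not required, and no split by needle experience is planned

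*Combined protocol and SAP*

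**What the plan says.** All places are in the combined protocol and SAP.

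- **Patient Survey:** "Participants will be given a survey at each visit", and one of its aims is to "assess experience and preference over conventional needle and syringe". The Study Timeline table marks it at baseline and weeks 4, 8 and 12. Neither place limits the preference item to children who have had needle injections.
- **Study Design:** the study assesses "needle-free delivery administration of ILTA with the Med-Jet as an alternative to conventional syringe and needle". The needle is named as the method to be replaced, not as a study arm.
- **Intervention (under Prior and Concomitant Medications and Therapies):** "Only one of the alopecic patches will be treated". The syringe in the procedure loads the device: "This syringe will be attached to the Med-Jet along with a sterile barrel and disposable sterile tip".
- **Inclusion and Exclusion Criteria:** the relevant requirement is "Patient is a candidate for intralesional triamcinolone". Past ILTA is not required.
- **Study Visits, Visit 1:** staff will "obtain medical history (medical conditions, surgeries, alopecia areata history" and other items. The section on prior and concomitant therapies adds that all alopecia areata therapies are recorded. Neither names needle-delivered ILTA as a specific field.
- **Data Analysis Plan:** generic tests and a 0.05 cutoff are given. The survey is not mentioned.

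**The concern.** With no needle arm, this item is the only place where participants compare the jet with the method it is meant to replace. A child who has had needle ILTA can compare two procedures. A child who has not can compare the jet only with an expectation, or with some other needle such as a vaccination. These are different quantities, and nothing in the plan keeps them apart.

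A single percentage preferring the Med-Jet is likely to be read as a head-to-head preference and carried into the case for a larger trial. The Background section says that fear of injections and pain often limit ILTA in children, so some may enrol without needle ILTA because they avoided it. Their answers would then reflect that fear as well as the device.

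**Working it through.** **Step 1: does any child receive a needle injection in the study?** One patch is treated, and the only procedure described is the Med-Jet procedure. The comparator patch in the Rule of Thumb assessment is therefore untreated, not needle-injected. A training sentence in the Intervention text mentions the syringe and the needle-free system together, but no needle procedure follows it. The answer is no.

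**Step 2: must a child have had needle ILTA before?** Candidacy is the only requirement. Recruitment by clinic, database letter, records search, referral and flyer does not select for it. Exclusion criterion 7 concerns only treatment started less than 4 weeks before screening, so children on an established regimen can enter. A mixture of experienced and inexperienced children is plausible. Its proportions are not given.

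**Step 3: is a split by experience planned?** None is stated in the Patient Survey section or the Data Analysis Plan.

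**Step 4: how far could the mix move the figure?** The plan gives no preference figure to reproduce. The only input from the documents is n = 15 (Number of Research Participants). Let m be the number of experienced children, and let pE and pN be the shares preferring the jet among experienced and inexperienced children. All three are assumptions.

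Combined share = [m·pE + (15 − m)·pN] / 15

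| m | pE = 50%, pN = 90% | pE = 70%, pN = 90% |
|---|---|---|
| 3 | (1.5 + 10.8)/15 = 82% | (2.1 + 10.8)/15 = 86% |
| 5 | (2.5 + 9.0)/15 = 77% | (3.5 + 9.0)/15 = 83% |
| 10 | (5.0 + 4.5)/15 = 63% | (7.0 + 4.5)/15 = 77% |
| 12 | (6.0 + 2.7)/15 = 58% | (8.4 + 2.7)/15 = 74% |

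The experienced children's preference is constant within each column, yet the combined figure moves by 24 points (82 − 58) in the first and 12 points (86 − 74) in the second. The sign depends on the assumption. With the first pair reversed (pE = 90%, pN = 50%), m = 3 gives (2.7 + 6.0)/15 = 58%, which understates the experienced preference.

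**Step 5: what does separate reporting cost in precision?** Exact (Clopper-Pearson) 95% limits for x of n are the 0.025 quantile of Beta(x, n − x + 1) and the 0.975 quantile of Beta(x + 1, n − x). For an assumed 80% preference:

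| Children counted | x/n | Exact 95% interval |
|---|---|---|
| All 15 | 12/15 | 52% to 96% |
| 10 experienced | 8/10 | 44% to 97% |
| 5 experienced | 4/5 | 28% to 99% |

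Every row has the same point estimate, so this table shows loss of precision only. It says nothing about bias.

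**The case against.** Several objections have force.

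- **Pooling is not a stated rule.** A reader might infer that the plan pools all answers. It does not say so; the analysis of the survey is simply unspecified. What stands is that nothing prevents a combined figure, which is the default when no split is written down.
- **The survey form is not in the documents.** The survey's mention of experience may mean that it asks about past needle use or offers a never-had option. That would ease the split, but no planned use of such an answer is stated.
- **Much of the data may be captured already.** Alopecia history and therapies are recorded, and prior ILTA should fall within them. The needle route is not named, though, and a split chosen after seeing 15 answers is less credible than one fixed beforehand.
- **The survey asks about needle and syringe in general.** The rationale includes needle fear as such, so a child's knowledge of other needles has some relevance. This is a good reason to keep the item for everyone. It does not turn those answers into a comparison with needle ILTA.
- **The bias is not demonstrated.** A reader might infer that a needle-fearful child without ILTA experience can answer only one way, so the figure must favour the device. That does not follow: after treatment such a child may find the jet painful or frightening and prefer neither method, or the needle.
- **The experienced group is not ideal either.** These children compare from memory, and some may join a needle-free study because needles went badly. Separate reporting makes the figure interpretable but does not create a randomised comparison.

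**Conclusion.** The point holds as a minor one about reporting and interpretation. Every child is asked a comparative question, the study supplies only one side of the comparison, the other side is not required from the past, and no split is planned. A combined preference figure would depend on an uncontrolled case mix: by 12 to 24 percentage points in the examples, all of which rest on assumed shares and an assumed number of experienced children. The direction probably favours the device, because fear of needles can shape the answers of children who have not had needle ILTA, but no figure in the documents establishes it.

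A reader might also infer that the study's tolerability conclusion is compromised. The documents do not support that. Preference is not named in the Objectives or in the Study Design hypothesis; Data to be Collected lists the pain score as the tolerability measure and places the survey under quality of life; and the sample size section concerns mild versus moderate pain. Pain, efficacy and safety results do not depend on this item.

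**What to change.** 1. Within the alopecia history and therapies already taken at screening, add one field: prior needle-delivered ILTA, yes/no, with date.
2. Keep the preference item, and all other survey items, for every child.
3. Add one sentence to the Data Analysis Plan: preference is reported separately by prior needle ILTA; answers from children without it are labelled expected preference; and any statement of preference over needle ILTA rests on the experienced group, as a count with its exact 95% interval.
4. Note with the result that the experienced children compare from memory.

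The cost is one field and one sentence. Visits, procedures, eligibility and sample size do not change. The downside is a smaller denominator and a wider interval for the experienced group, as the 5-child example shows, and the group may turn out very small. If so, the count should be given without a claim.
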